#### **4.1.9.3. Urinalysis**

Urinalysis will be conducted at screening. Additional testing will be conducted on study visit Week 12 (Day 84) and Week 24 (Day 168)/Early Termination. Repeat testing at follow-up visit Week 28 (Day 196) will only be performed if abnormal clinically significant values are obtained at the Week 24 (Day 168) visit.

Urinalysis will include: nitrite, Na, K, Ca, P, Protein, RBC, WBC, blood, glucose, ketone bodies, bilirubin (conjugated), urobilinogen, urine specific gravity, osmolarity, and pH.

#### **4.1.9.4. Plasma Citrulline**

Testing of plasma citrulline value will be conducted at baseline in order to establish a baseline level. Additional testing will be conducted on study visit Week 12 (Day 84) and Week 24 (Day 168)/Early Termination.

#### **4.1.9.5. Blood Glucose Levels**

Blood glucose monitoring will be performed pre-dose at randomization (Day 0) and on Days 1, 2, and 3, and twice a week for the rest of the treatment period while hospitalized. If subjects are discharged home the test would be done on each visit once a week. In addition, any abnormality in blood glucose levels that would be captured outside of these tests, would also be reported. This is a part of standard monitoring conducted on this population.

#### **4.1.9.6. Anti-Insulin Antibodies**

Blood will be drawn to test for the presence of anti-insulin antibodies at baseline. Additional anti-insulin antibody testing will be conducted on study visit Week 12 (Day 84) and Week 28 (Day 196).

#### **4.1.10. Episodes of Significant Feeding Intolerance**

Episodes of significant feeding intolerance will be collected throughout the study period at baseline, randomization, initial treatment period (Days 1, 2 and 3), at each weekly study evaluation (at the institution) or visit, if discharged, through Week 12, and Week 24.

Significant feeding intolerance is defined as:

- The need to hold enteral feeds for 24 hours.

Reasons or requirements to hold feedings may include, but are not limited to, the following:

- Increased stool output (compared to the previous 24 hours or leading to perianal excoriation)

- Increased vomiting (associated with residuals of previous feeds, bilious vomiting, increase of volume of regurgitation or number of events of emesis compared to the previous 24 hours).
- Abdominal distention (leading to abdominal pain with respiratory compromise)

#### **4.1.11. Concomitant Medication**

All concomitant medication given within 30 days prior to study entry will be documented. Dietary supplements, prescription drug, and non-prescription drugs will be listed at screening, at baseline, randomization, and at each visit through the Week 28 (Day 196) assessment. After week 28, only clinically significant medications that are used to treat potential adverse effects of NTRA-9620 will be recorded at 52 and 104 weeks. The investigator will assess the clinical significance of the medication use. Each entry will include the treatment's start date, medication/treatment name (generic), indication for use, dosing regimen (dose and frequency of use), route of administration, and stop date (if applicable) or ongoing. Study subjects will be routinely assessed for changes in the administration of concomitant medication during the trial.

Subjects may not receive the following medications while on study:

- Systemic insulin administration unless an acute life-threatening event occurs.
- Other investigational drugs or growth factors and glutamine.
- Pancreatic enzymes (replacement therapy).

Cholestyramine, if given, should be administered 2 hours apart from study medication because of its potential to absorb insulin.

Any concomitant medication and its potential to interfere with the study medication will be discussed with the investigator.

#### **4.1.12. Long-Term Follow-Up Visits**

Follow-up evaluations will be conducted at 52 and 104 weeks after initiation of treatment. Each follow-up visit during the safety follow-up period will include body weight, body length, head circumference, parenteral nutrition intake, enteral nutrition intake, re-hospitalizations and adverse events.

In this patient population, SOC visits are routine and may occur before the scheduled study visits on weeks 52 and 104. Thus, any available clinical data on body weight, body length, head circumference, parenteral nutrition intake, enteral nutrition intake, re-hospitalizations and adverse events will be documented and entered in the Unscheduled Visit form and entered into the eCRF. These data will include neurodevelopmental Bayley's score cognitive, language and motor domains at 2Y corrected age (details of neurodevelopment assessment are included in [Appendix D](#)). If such a routine Standard of Care visit is not conducted or complete data is not collected as part of these visits, these will not be considered missing data.

In the interim, scheduled telephone calls will be made to the patient and the family every three months after week 28.

#### **4.1.13. Adverse Events (AEs)**

The information obtained during study visits, physical examinations, vital signs measurements, blood testing, and by any other means will be evaluated in light of baseline medical data and thus provide the basis for identification and grading of AEs.

The AEs reported during the trial will be graded (see Section [7.1](#)), documented, and assessed in light of their clinical significance and relation to investigational product. In addition, the following information regarding the AE must be obtained and recorded in subject's source document and Case Report Form (CRF): AE description, start date, end date (if applicable) or ongoing, severity, seriousness, investigator's assessment of the relationship of the AE to study drug, outcome (i.e., resolved, resolved with sequelae, ongoing, death due to this AE, death due to other events, unknown) and action taken (e.g., concomitant medication). Information regarding occurrence of AE monitoring will be captured throughout the study, from Day 7 (initiation of dosing) 28 days after the final primary study visit at Week 28 (Day 196). AEs considered treatment related by the Investigator will be documented after the primary study completion on Week 52 (Day 364) and Week 104 (Day 728) to assess any potentially related adverse outcomes of treatment and re-hospitalizations. Pre-treatment emergent events will not be considered as AEs, but will be recorded as medical history.

Prior to this current trial, four clinical trials including three in preterm infants and one in SBS infant subjects have been performed with oral administration of insulin. No treatment-related adverse events have been reported and no systemic absorption of insulin has been detected.

#### **4.1.14. Evaluation of Response**

##### **4.1.14.1. Parenteral Nutrition (PN) Intake**

PN intake will be obtained at screening, baseline, randomization, and at each study visit (as described in [Appendix B](#)). In case of an acute medical event during the study period the patient will be clinically stable before study visit occurs. The total volume and the caloric value of parenteral nutrition administered will be recorded in each study visit. The daily total amount of PN/IV, and number of hours per day on PN/IV will be entered into the CRF. For patients discharged home a diary will be provided to confirm prescribed PN and EN intake.

##### **4.1.14.2. Enteral Nutrition (EN) Intake**

EN intake will be obtained at screening, baseline, randomization, and at each study visit (as described in [Appendix B](#)). In case of an acute medical event during the study period the patient will be clinically stable before study visit occurs. The total volume and the caloric value of enteral nutrition administered will be recorded in each study visit. The daily total amount of EN

and caloric content will be entered into the CRF. For patients discharged home a diary will be provided to confirm prescribed EN and PN intake.

Solids intake information will be collected at the site level and reported by the investigator as part of enteral intake in the CRF.

Negligible amounts of breast milk/formula/solids intake that are only provided for stimulation of suck and swallow coordination and not used as part of the calculations for providing adequate caloric needs for growth will not be calculated as part of daily enteral intake.

## **4.2. STUDY VISITS**

### **4.2.1. Screening Procedures**

All information collected and documented during screening procedures will be reviewed to ensure that the subject satisfies eligibility requirements as described by the study inclusion and exclusion criteria. This information will be fully documented in the subject's file.

The Screening Visit will be performed at a minimum 7 days prior to the Baseline Visit. Study screening procedures will include the following:

- Informed Consent - Section [4.1.1](#)
- Medical History and Demographics - Section [4.1.2](#)
- Maternal Data - Section [4.1.3](#)
- Physical Examination - Section [4.1.4](#)
- Weight and Body Length - Section [4.1.5](#)
- Head Circumference - Section [4.1.6](#)
- Vital Signs - Section [4.1.7](#)
- EKG - Section [4.1.8](#)
- Clinical Laboratory Tests - Section [4.1.9](#) (as applicable within Section [4.1.9](#))
- Concomitant Medication Listing - Section [4.1.11](#)
- PN/IV and EN Intake - Sections [4.1.14.1](#) and [4.1.14.2](#)

### **4.2.2. Baseline**

All information collected and documented during baseline procedures will be reviewed to ensure eligibility in reference to study inclusion and exclusion criteria, and fully documented in the subject's file.

The interval between the signing of the consent (Screening Visit) and the Baseline Visit is considered the baseline period. It is defined as a minimum of 14 days prior to the

Randomization Visit. During this period, data will be collected on PN/IV and EN use that will be used for calculating the baseline %PN and to confirm eligibility. All assessments will be performed and recorded for each day of baseline, except for plasma citrulline and anti-insulin antibodies that will be conducted and recorded on the last day of baseline, 0-1 day prior to the randomization visit. Baseline procedures will include the following:

- Weight and Body Length - Section [4.1.54.1.5](#)
- Vital Signs - Section [4.1.7](#)
- Plasma Citrulline - Section [4.1.9.4](#)
- Anti-insulin Antibodies - Section [4.1.9.6](#)
- Episodes of significant feeding intolerance - Section [4.1.10](#)
- Concomitant Medication Listing - Section [4.1.11](#)
- PN/IV and EN Intake - Sections [4.1.14.1](#) and [4.1.14.2](#)

#### **4.2.3. Randomization**

Once qualified for the study, subjects will be randomized in a 1:1:1 ratio to 2 IU/kg of NTRA-9620 or to 1 IU/kg of NTRA-9620 or matching placebo. Randomization should take place as close as possible to treatment initiation and not more than 24 hours before the first dose of study drug. Randomization, which will be done centrally, will be stratified by length of small intestine ( $L < 50\%$  or  $50\% \leq L \leq 70\%$ , L is the length remaining compared to expected length for gestational age [\(13\)](#)) and presence or absence of an ileocecal valve.

The study has recruitment goals aimed at randomizing at least 30 subjects with < 50% remaining length of small intestine for gestational age and at least 30 subjects born prematurely. During the course of the study, Nutrinia or its designees will monitor recruitment of subjects with < 50% remaining bowel and of premature infants. If the goal of 30 subjects with < 50% remaining bowel is unlikely to be achieved, Nutrinia will consult appropriate Regulatory Authorities and may increase the sample size of the trial to ensure enrolling at least 30 subjects with < 50% bowel remaining.

The randomization and baseline visits are expected to occur at the same visit. However, in some instances the logistical complications at the investigative site may require these visits to be up to 24 hours apart. All information collected and documented during the randomization visit will be reviewed prior to randomizing the subjects to ensure the subject meets study inclusion and exclusion criteria. The information will be fully documented in the subject's file.

The following data will be collected at the randomization visit:

- Weight and body length - Section 4.1.5
- Head circumference - Section 4.1.6
- Vital signs - Section 4.1.7
- Blood glucose level - Section 4.1.9.5
- Episodes of significant feeding intolerance - Section 4.1.10
- Concomitant medication Listing - Section 4.1.11
- PN/IV and EN intake - Sections 4.1.14.1 and 4.1.14.2

#### **4.2.4. Study Treatment**

NTRA-9620 is an insulin-based drug product intended to enhance bowel adaptation, promote EN, and reduce dependence on PN/IV. NTRA-9620 consists of maltodextrin (MD) and recombinant human insulin in powder form for reconstitution.

Subjects will receive SOC PN/IV and enteral feedings containing either dose of NTRA-9620 or matching placebo. NTRA-9620 will be dosed to target an insulin dose of 4 IU/kg/day or 8 IU/kg/day for 24 weeks. NTRA-9620 and matching placebo can be reconstituted in normal (0.9%) or half normal (0.45%) saline (NaCl) and can be administered concomitantly with SOC infant formula, donor breast milk, or mother's milk used for enteral feeds. During hospitalization, NTRA-9620 or matching placebo will be dosed 4 times a day as bolus administration spaced as equally over 24 hours as possible (ideally at every six hours, but no less than 3 hours between any two doses). In home care setting, subjects will receive NTRA-9620 or matching placebo four times a day (ideally at every six hours, but no less than 3 hours between any two doses).

#### **4.2.5. Subject Site Visits**

Subject site visits will be performed as follows:

- For study Days 1 to 84, the study day window will be  $\pm$  2 day.
- For study Days 98 to 168, the study day window will be  $\pm$  7 days.
- For study days after Day 196, the study day window will be  $\pm$  14 days.
- Subject site visits will include procedures as described in [Appendix B: Schedule of Study Procedures](#).
- For site visit that results in study discontinuation, see termination visit in Section 4.2.6.

#### **4.2.6. Visit and Early Discontinuation from Study Medication Visit**

If a subject prematurely discontinues study medication, all reasonable measures will be taken to perform an Early Discontinuation from Study Medication Visit (Week 28 visit). This visit should include all procedures listed in the schedule of events Follow Up (Final Primary Study Visit) for Week 28 (Day 196). These procedures are necessary to complete subjects' records: physical examination, weight, body length, head circumference, vital signs, clinical laboratory test (only if clinically significant values were obtained at the Day 196, or if terminated earlier), anti-insulin antibodies, plasma citrulline (only if terminated before Day 168), parenteral nutrition intake, enteral nutrition intake, concomitant medication, adverse event, and updating of subject contact information.

All reasonable efforts will be made to perform a termination visit (Week 28) in patients who discontinue early.

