
Study Visit Schedule (See Appendix B: Schedule of Study Procedures)
	
Subjects diagnosed with SBS resulting from surgical resection may be evaluated for qualification to this study after their parent(s) or legal guardian(s) have given written informed consent. Screening assessments will include medical history and demographics, inclusion and exclusion criteria, maternal data, weight and body length, head circumference, vital signs, electrocardiogram (EKG) in triplicate, physical examination, urinalysis, hematology, blood chemistry, PN intake, EN intake and concomitant medications.
 
During the 24-week treatment period, subjects are expected to be on PN/IV for all or most of the treatment period and thus are expected to be hospitalized for approximately 12 weeks, but they may be released sooner according to local institution's SOC. Each subject will receive the study treatment 4 times daily concomitantly with enteral feedings. Treatment will continue for the full 24 weeks regardless of the %PN (i.e., treatment should be continued even if subject is weaned off PN). EN includes SOC infant formula, donor breast milk, or own mother's milk (as detailed in Appendix A).
 
Once the subject is released for home care, the caregivers, including any at-home medical professionals, will be trained on the proper procedures for dosing NTRA-9620 or matching placebo and how to record study information in the daily diary. Dose interruptions over the 24 week study treatment period will only be allowed at investigator discretion (i.e., NPO for procedure.) No dose interruption should last more than 7 consecutive days. During the first 12 weeks where the subject is likely to be hospitalized, there should be no more than 10 days of dose interruption. During weeks 12 to 24, where the subject may be at home or at a secondary facility, there should be no more than 15 days of dose interruption.
 
During the study, the investigator will follow a recommended PN/IV and EN feeding protocol (Appendix A).
 
Both the volume and the caloric value of PN/IV and EN consumed will be recorded at each study visit (as described in, Appendix B). Vital signs, body weight, body length, head circumference, and gastric residuals (through Week 12 only if it is done as part of the SOC), adverse events, and concomitant medications will be collected by weekly assessments throughout Week 12 and at least once every two weeks between Week 12 and Week 24. In addition, at Week 12, assessments will include full physical examination, hematology, chemistry, urinalysis, anti-insulin antibodies, and plasma citrulline. The non-routine use of oral antibiotics and probiotics are allowed if it is part of the SOC. Recording of parenteral and enteral nutritional intake will be continued until the end of the 24-week treatment period.
 
Once released for home care, the subject will return to the clinic as needed according to standard medical practice or at least every two weeks between Week 12 and Week 24 for assessments, replenishment of study medications, and adjustment of the PN/IV and EN protocols.
 
At the end of the treatment period (Week 24) subjects will discontinue administration of study medication. At this time, subjects will be given a full physical examination. Assessments will include body weight, body length, head circumference, vital signs, hematology, chemistry, urinalysis, plasma citrulline, concomitant medications, PN, EN and AEs.
 
The primary portion of the study will be considered complete when the last randomized subject finishes the 24 week treatment period and a 4 week initial safety follow-up period (Week 28). At Week 28, the same assessments as in Week 24 visit will take place, except for plasma citrulline. In addition, anti-insulin antibodies will be assessed.
 
Additional long-term safety and follow-up evaluations will be conducted at 52 and 104 weeks after initiation of treatment. Each visit during the follow-up period will include body weight, body length, head circumference, parenteral nutrition intake, enteral nutrition intake, re-hospitalizations and adverse events. In addition, growth parameters and nutritional support information from routine care visits at the primary site will be recorded in the eCRF. These data will include Bayley's neurodevelopmental cognitive, language and motor domains at 2Y corrected age.

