All subjects will receive SOC PN/IV and enteral feedings containing NTRA-9620 or matching placebo. NTRA-9620 or matching placebo will be dosed to target an insulin dose of 1 IU/kg or 2 IU/kg administered four times a day, spaced as equally over 24 hours as possible (ideally at every six hours, but no less than 3 hours between any two doses). The study medications can be reconstituted in normal (0.9%) or half normal (0.45%) saline (NaCl) and administered concomitantly with SOC infant formula, donor breast milk, or own mother's milk (OMM) used for enteral feeds. During the hospitalization period, dosing will be performed as a bolus administration four times a day. In home care, subjects will receive NTRA-9620 or matching placebo four times a day as well.

Subjects will continue treatment for the full 24 weeks of dosing regardless of the %PN use (i.e., even if subject is weaned off PN). Dose interruptions over the 24 week study treatment period will only be allowed at investigator discretion (i.e., nothing by mouth (npo) for procedure.) No dose interruption should last more than 7 consecutive days. During the first 12 weeks when the subject is likely to be hospitalized, the subject should experience no more than 10 days of dose interruption. During weeks 12 to 24, when the subject may be at home or at a secondary facility, the subject should experience no more than 15 days of dose interruption. The daily PN and EN intake for each subject will be recorded in a study diary. Subjects will be assessed weekly or once every two weeks as described on the Schedule of Study Procedures ([Appendix B](#)) for the treatment period. Most subjects will remain hospitalized for at least 12 weeks to collect accurate PN amounts, but some may be released from the institution per local SOC. Subjects will continue treatment for the full 24 weeks of dosing regardless of the %PN use (i.e., even if subject is weaned off PN). Enteral nutrition includes SOC infant formula, donor breast milk, or own mother's milk (as detailed in [Appendix A](#)). Subjects will continue on SOC feedings after the 24 week intervention period. A final study statistical analysis of efficacy and safety will be conducted at Week 28, 4 weeks after the end of dosing. All subjects will be further followed for long-term safety through Week 104; these safety data will be reported as an addendum to the final clinical study report.

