## **5.2. PREMATURE DISCONTINUATION FROM STUDY MEDICATION**

Subjects will be discontinued from the study medication after evaluation by the investigator and sponsor's medical monitor in any of the following cases:

- Any CTCAE Grade 3 or 4 adverse event (see Section 7) that the investigator considers related to study medication and not attributable to the underlying disease or considered common events listed in [Appendix C](#).
- Systemic hypersensitivity reaction related to study medication.
- Non-compliance of the subject's parent(s) or legal guardian(s) with study procedures
- Other reasons regarded as warranting subject's discontinuation from study medication.
- Premature study termination as described in Section 5.3.

Parent(s) or legal guardian(s) who voluntarily have their child discontinue the study medication will be questioned to determine whether an AE contributed to the decision to discontinue study medication.

Subjects who are withdrawn from treatment because of an adverse event will be followed and treated by the investigator until the abnormal parameter/condition or symptom has resolved or stabilized or the investigator deems further observations or examinations no longer required as medically indicated.

The investigator will make reasonable attempts to provide a reason for a subject's being withdrawn from study medication. The reason for the subject's withdrawal from study medication will be described in the subject's source documents and CRF

Subjects who prematurely discontinue will have an Early Discontinuation for Study Medication Visit as described in Section 4.2.6□ . Subjects who discontinue study medication early should return four (4) weeks after study medication discontinuation to receive follow-up visits.

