## **5.3. PREMATURE DISCONTINUATION FROM STUDY**

Participation in the study is strictly voluntary. In accordance with the current revision of the Declaration of Helsinki, parent(s) or legal guardian(s) of subjects have the right to withdraw their child from the study at any time, for any reason, specified or unspecified, and without prejudice to any future medical care by the physician or the institution. If the parent(s) or legal guardian(s) of subjects choose to withdraw their child, the investigator and the Sponsor must be informed immediately.

The subject will be withdrawn from the study if the parent(s) or legal guardian (s) withdraws consent.

The investigator will make reasonable attempts to provide a reason for withdrawal of subjects from the study. The reason for the subject's withdrawal from the study will be specified in the subject's source documents and CRF. When a parent or guardian asks to withdraw consent, the investigator should confirm that the parent/guardian understands the difference between withdrawal of study medication and withdrawal from the study. If the parent/guardian is willing to withdraw the subject from study medication but remain in the study, then the investigator should follow procedures in Section 4.2.6.

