- a. The final study day for purposes of the trial statistical analysis and Clinical Study Report (CSR) is Day 196. Subjects will be further followed long-term for safety to evaluate growth and nutritional intake as well as potential related adverse events through Day 728.
- b. If a subject prematurely discontinues study medication, all reasonable measures will be taken to perform an Early Discontinuation from Study Medication Visit (Week 28 visit). This visit should include all procedures listed in the schedule of events Follow Up (Final Primary Study Visit) for Week 28 (Day 196). These procedures are necessary to complete subjects' records: physical examination, weight, body length, head circumference, vital signs, clinical laboratory test (only if clinically significant values were obtained at the Day 196, or if terminated earlier), anti-insulin antibodies, plasma citrulline (only if terminated before Day 168), gastric residuals (only if terminated before Day 84 and if part of SOC), parenteral nutrition intake, enteral nutrition intake, concomitant medication, adverse event, and updating of subject contact information.
- c. If routine Standard of Care Visits are conducted this data, if collected will be entered as an unscheduled visit. The data to be included, if collected, is body weight, body length, head circumference, parenteral nutrition intake, enteral nutrition intake, re-hospitalizations and adverse events. If these routine SOC visits are not conducted with these procedures, these will not be considered missing visits. These data will include neurodevelopmental Bayley's score cognitive, language and motor domains at 2Y corrected age. After Week 28 (Day 196), a follow up phone call every 3 months as part of long-term follow up.
- d. A complete physical examination at screening and on Day 84 (Week 12), Day 168 (Week 24), and Day 196 (Week 28). A limited problem-oriented physical examination will be performed on each visit between Week 12 (Day 84) and Week 24 (Day 168): Days 98, 112, 126, 140, and 154, if needed.
- e. Any event that occurs before study drug dosing will be recorded as medical history, including but not limited to present medical conditions, concomitant non-drug treatments and hypersensitivity to drugs.
- f. Infant's mother will be collected including age, medical history of any congenital abnormalities and complications during gestation or delivery.

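### The protocol does not say whether an infant who stops study drug but stays in the trial keeps the Appendix B visits and daily intake recording, so a measurable co-primary value may end up imputed

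*Combined protocol and SAP*

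**What the plan says.** **Text on infants who stop study drug.** Section 5.3 separates stopping drug from leaving the study. If a parent is willing to "withdraw the subject from study medication but remain in the study, then the investigator should follow procedures in Section 4.2.6". Section 4.2.6 then describes an early-discontinuation visit: "This visit should include all procedures listed in the schedule of events Follow Up (Final Primary Study Visit) for Week 28 (Day 196". The same section adds: "All reasonable efforts will be made to perform a termination visit (Week 28) in patients who discontinue early". Section 5.2 sets the timing: "Subjects who discontinue study medication early should return four (4) weeks after study medication discontinuation to receive follow-up visits". Appendix B footnote b largely repeats Section 4.2.6 and makes some procedures conditional: "plasma citrulline (only if terminated before Day 168), gastric residuals (only if terminated before Day 84 and if part of SOC".

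Section 4.2.6 also serves infants who leave the study altogether. Section 4.2.5 says: "For site visit that results in study discontinuation, see termination visit in Section 4.2.6".

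**General text on intake recording.** Section 3.1: "The daily PN and EN intake for each subject will be recorded in a study diary". Synopsis, Study Visit Schedule: "Recording of parenteral and enteral nutritional intake will be continued until the end of the 24-week treatment period". Neither sentence is limited to infants on drug, and neither refers to Section 4.2.6.

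**Use of the data.** The co-primary values are averages over Days 78–84 and Days 162–168 (Section 8.3.2). The Full Analysis Set is every randomized infant, analysed by randomized arm (Section 8.2.2). An infant with no data for a time point has the value multiply imputed (Section 8.1.3).

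**The concern.** The visit prescribed for a drug-stopper who stays in the study carries the name and content of the last visit of the primary study, and is elsewhere called a termination visit. A site reading only Section 4.2.6 could reasonably conclude that the primary schedule is finished for that infant. A site reading Section 3.1 would carry on recording. The protocol does not say which is meant.

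At stake is the completeness of the co-primary data in the Full Analysis Set. These infants are still available and their %PN at Weeks 12 and 24 can be measured. If recording stops, an imputed value replaces one that could have been observed, and whether that happens may depend on the site. The SAP can choose the imputation model but cannot make a site record intake. The home diary is the most exposed source, because a family told that the final visit is done may stop keeping it.

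**Working it through.** This is a question of what the text requires, so the passages come first and the arithmetic only illustrates.

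**1. Does any text end follow-up for these infants?** No. No sentence cancels the remaining Appendix B visits.

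**2. Does any text continue it?** Not specifically. Sections 4.2.6, 5.2 and 5.3 and footnote b are the places that deal with drug-stoppers, and none mentions the remaining visits or intake recording up to Day 168. The synopsis rule runs to the end of the 24-week treatment period, which a site could read as over once treatment stops. Section 3.1 covers each subject without exception.

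**3. Does the four-week return cover the endpoint windows?** Only by coincidence, because it is timed from the stop day. Assume that the return is the Section 4.2.6 visit, that the site drops the other visits, and that daily intake is recorded up to that visit, so that the last recorded day = stop day + 28.

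- At least one day in Days 78–84: stop + 28 ≥ 78, so stop ≥ Day 50.
- At least one day in Days 162–168: stop + 28 ≥ 162, so stop ≥ Day 134.
- Hence a stop before Day 50 loses both windows, a stop on Days 50–133 loses Week 24 only, and a stop from Day 134 loses neither.

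Variations on these assumptions:

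- Section 8.1.3 speaks of a 10-day period, whereas the endpoint uses 7 days. If the 10 days are Days 75–84 and 159–168 (assumption), the cut-offs become 75 − 28 = Day 47 and 159 − 28 = Day 131.
- If recording ends with the last dose, the cut-offs are Days 78 and 162, except where the visit itself falls in a window: stops on Days 50–56 (visit on Days 78–84) or Days 134–140 (visit on Days 162–168).
- Appendix B gives the Day 196 visit a window of ±7 days. Applied to this visit, it would move the Day 50 and Day 134 cut-offs by up to 7 days either way, to Days 43–57 and Days 127–141.
- If the site keeps the Appendix B visits and daily recording, no value is lost whatever the stop day.

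**4. How many infants?** Section 8.1.3 expects about 10% not to reach Week 12 and an additional 10% not to reach Week 24:

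- Week 12: 0.10 × 150 = 15.
- Week 24: (0.10 + 0.10) × 150 = 30.

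These are not counts of the infants at issue. The stated reasons include death as well as necrotizing enterocolitis and other complications, and the section does not say how many will have stopped drug while remaining in the study. No drug-stop rate is given anywhere, so the number affected cannot be derived.

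**5. What would continued follow-up involve?** After a stop at Day 42, the visits left through Day 168 are Days 49, 56, 63, 70, 77, 84, 98, 112, 126, 140, 154 and 168: 12 visits. After a stop at Day 84 they are Days 98, 112, 126, 140, 154 and 168: 6 visits.

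**The case against.** The strongest reply is that the default already protects the data. With no sentence cancelling the schedule, an infant still in the study stays on it. Section 3.1 applies to each subject, and Section 5.3 makes the investigator explain the difference between leaving drug and leaving the study, a distinction with little purpose if follow-up then stops. The termination wording can be put down to the infants who leave the study and are sent to the same section. This is a fair reading and may be what the sponsor intends. It does not remove the gap, because the drug-stopper text itself neither says so nor points to the general rules.

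There are also recovery routes. Infants are expected to be in hospital for about 12 weeks (Section 3.1), so Week 12 intake will often be in the chart. The home diary serves to confirm prescribed intake (Section 4.1.14.1), so the prescription is a second source. Section 4.2.8 allows unscheduled visits at the sponsor's request to complete missing results. These may recover some values, but they are discretionary or partial, and a diary that was not kept cannot be recreated.

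Three stronger readings are tempting and are not supported:

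- **That the protocol orders follow-up to stop, or allows one visit only.** Section 5.2 uses the plural for the follow-up visits, and nothing withdraws the Appendix B schedule.
- **That 15 values at Week 12 or 30 at Week 24 could be rescued.** That forecast includes deaths and does not count drug-stoppers who stay in the study.
- **That the result would be biased in a known direction.** The imputation details are left to the SAP, and neither the number of stoppers nor their split by arm is known.

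**Conclusion.** The concern holds as an unreconciled instruction, not as a stated decision to stop measuring. Sites may follow drug-stoppers differently, and a site that treats the Section 4.2.6 visit as the end of the primary study may leave a measurable Week 12 or Week 24 value to be imputed. The loss ranges from none, if all sites keep the schedule, to an unknown number. The stop-day cut-offs in the working depend on assumed site behaviour that no document describes; they show which infants would be exposed and do not show that loss will occur.

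This is worth correcting because it determines what is collected on the co-primary endpoint in the Full Analysis Set, and because later analysis cannot supply intake that was never recorded. It is a cheap improvement to conduct and no reason to doubt the design. Confidence is medium, since the sponsor may already intend continued recording.

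**What to change.** In Section 4.2.6 and Appendix B footnote b, with a matching sentence in Section 5.2, state: *Infants who stop study drug but remain in the study keep the Appendix B visits, with daily PN/IV and EN intake recorded, through Day 168. The visit four weeks after the last dose is additional and does not replace any scheduled visit.*

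For families who decline the visits, collect at least a 7-day chart or diary record of intake for Days 78–84 and for Days 162–168.

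A sentence in Section 8.1.3 confirming that intake measured off drug is used in the Full Analysis Set would be optional clarification. Sections 8.2.2 and 8.1.3 already imply it, since the set includes all randomized infants and only those with no data are imputed.

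**Cost.** A few sentences of protocol text. Families of drug-stoppers keep visits that are already scheduled (12 after a stop at Day 42, 6 after a stop at Day 84), or in the minimum version provide at most two 7-day records. Nothing is added beyond Appendix B and the four-week return that Section 5.2 already asks for. Some families may decline even so. The change has to be made prospectively.
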